### 7.7.7 IVL Device Crossing Failures

If the investigator is not able to advance the IVL Catheter across the target lesion after exhausting pre-dilatation efforts **AND** no pulses were delivered, this will be defined as a Device Crossing Failure. Any further treatment will be done per standard of care without the use of IVL. In the case of a Device Crossing Failure, the subject is considered enrolled; but as treatment with IVL did not occur, will be exited from the study following hospital discharge.

However, if the investigator *cannot fully cross the target lesion with the IVL catheter and pulses were delivered, this is not considered a device crossing failure.* Under those circumstances, a subject is considered enrolled and follow up is required through 24 months (see Protocol Section 7.4, Schedule of Events and Evaluations.)

Note:

- Device crossing failures and devices that did not fully cross still should be documented as a device deficiency/malfunction.
- Use of IVL (i.e., for the purpose of enrollment of lesion/subject) is not permitted if non-conventional PTA treatments -- including atherectomy, laser or cutting/scoring balloons -- were previously used to treat the target lesion.

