#### **7.7.5 Definition of Enrollment**

The definition of enrollment is when the subject signs informed consent, meets all general & angiographic eligibility criteria, and the IVL catheter has been inserted over a 0.014" guidewire (which had been previously passed across the target lesion).

	No.: CP 65007	REV. C
	TITLE: Disrupt PAD BTK II Study	
	CLASS: CLINICAL PROTOCOL	PAGE 32 OF 71

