### 9.1 General Statistical Methods

Descriptive statistics will be provided in this clinical study. Analyses will be conducted at pre-specified time points including 30 days, 6, 12 and 24 months.

Categorical variables will be summarized by the number of observations available, frequency, and percentage. Unless otherwise noted, missing data will be excluded from the denominator. Comparisons will utilize a Chi-square test, or Fisher's exact test when 20% or more of expected cell frequencies are less than 5. Clinical outcomes analyzed at 30 days will be evaluated as categorical (binary) data. McNemar's chi-square may be used to assess within-subject changes in a bivariate response variable. Exact confidence intervals will be generated for estimates of proportions.

Continuous variables will be summarized by the mean, standard deviation, median, minimum, and maximum. Within-subject changes will be analyzed parametrically using the Paired t-test if the differences are normally distributed, or non-parametrically using the Sign-Rank Test if the differences are not normally distributed. Asymptotic confidence intervals will be generated for estimates of means.

Exploratory analyses and clarifications to the protocol specified analysis plan will be documented in the SAP. Statistical analyses will be performed using SAS System® Version 9.4 or higher.

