#### 9.2.1 Primary Safety Endpoint

The primary safety endpoint is Major Adverse Limb Events (MALE) or Post-Operative Death (POD) at 30 days defined as a composite of:

- all-cause death
- above-ankle amputation of the index limb
- major reintervention (new bypass graft, jump/interposition graft revision, or thrombectomy/thrombolysis) of the index limb involving a BTK artery

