### 9.4 Populations for Analysis

The primary analysis population will be the Intent-to-Treat (ITT) cohort which includes all enrolled subjects.

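### Device crossing failures are in the ITT cohort but leave the study after discharge, so their 30-day primary safety status is not collected

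*Combined protocol and SAP*

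**What the plan says.** **Who is enrolled.** Section 7.7.5 begins: "The definition of enrollment is when the subject signs informed consent, meets all general & angiographic eligibility criteria". The remaining condition is that the IVL catheter has been inserted over the guidewire. Delivery of IVL is not required. Section 15.1 adds that a lesion the device failed to cross remains a target lesion.

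**Who is analysed.** Section 9.4: "The primary analysis population will be the Intent-to-Treat (ITT) cohort which includes all enrolled subjects".

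**What happens to crossing failures.** Section 7.7.7 covers the case where the catheter cannot be advanced after pre-dilatation has been exhausted and no pulses were delivered. It says that "the subject is considered enrolled; but as treatment with IVL did not occur, will be exited from the study following hospital discharge". If the lesion was not fully crossed but pulses were given, the rule differs: "Under those circumstances, a subject is considered enrolled and follow up is required through 24 months". The note in the same section adds: "Device crossing failures and devices that did not fully cross still should be documented as a device deficiency/malfunction".

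**What is measured, and when.** Section 9.2.1: "The primary safety endpoint is Major Adverse Limb Events (MALE) or Post-Operative Death (POD) at 30 days defined as a composite of" three components, namely death from any cause, major amputation (above the ankle) on the treated side, and major reintervention. Table 1 (footnote 4) and Section 7.8.1 place the discharge assessment at 12 to 24 hours or before discharge, whichever is earlier. The next assessment is the 30-day visit (Section 7.8.2).

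**How missing outcomes are treated.** Section 9.1: "Clinical outcomes analyzed at 30 days will be evaluated as categorical (binary) data" and "Unless otherwise noted, missing data will be excluded from the denominator". Section 9.5 rules out imputation for the primary analyses; its censoring rule applies only to time-to-event analyses.

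**The concern.** The plan promises a 30-day safety proportion in all enrolled subjects, while its follow-up rule ends observation of some of them within days of the procedure. These subjects may go on to other treatment under standard of care, so death, amputation and reintervention before day 30 all remain possible. The loss is not random drop-out. It is required by the protocol and triggered by the device failing to cross, which the protocol itself has recorded as a deficiency or malfunction.

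At stake is the primary safety output, the MALE/POD proportion with its exact 95% confidence interval. A reader would take it to cover all enrolled subjects when part of that group was left out for a reason tied to device performance. Status that was not collected cannot be restored at analysis.

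**Working it through.** **Step 1. Follow one subject through the rules.** A subject consents, is eligible, has the catheter inserted, and the device does not cross.

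- Enrolled: yes (7.7.5, 7.7.7). In the ITT cohort: yes (9.4).
- Last scheduled assessment: 12 to 24 hours or before discharge (Table 1, 7.8.1). Events up to then are captured.
- From discharge to day 30: no visit or contact, because the subject has been exited (7.7.7).
- Event in hospital: the composite is met, so the subject can count in numerator and denominator.
- No event by discharge: day-30 status is unknown, so under 9.1 and 9.5 the subject most naturally leaves the denominator. If such subjects were counted as event-free instead, later events would be missed.

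Neither handling gives a 30-day proportion in all enrolled subjects.

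**Step 2. The plan's own figures.** The plan states no crossing-failure rate and no expected MALE/POD rate, so it has no safety figure to reproduce. The one related figure is the loss allowance in Section 9.3: 225 / (1 − 0.10) = 250, which allows for 250 × 10% = 25 lost subjects. That arithmetic is right. Precision is therefore not the issue.

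**Step 3. Size, under stated assumptions.** Take N = 250, c crossing failures exited event-free, and x events among the subjects followed. The reported estimate is x/(250 − c). The all-enrolled estimate lies between x/250 (none of the c has an event) and (x + c)/250 (all do). Intervals are Clopper-Pearson 95%.

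| Assumed x | Assumed c | Reported | All enrolled, none missed | All enrolled, all c had an event |
|---|---|---|---|---|
| 2 | 5 | 2/245 = 0.82% (0.10–2.92) | 2/250 = 0.80% (0.10–2.86) | 7/250 = 2.80% (1.13–5.68) |
| 2 | 25 | 2/225 = 0.89% (0.11–3.17) | 2/250 = 0.80% (0.10–2.86) | 27/250 = 10.8% (7.24–15.32) |
| 7 | 5 | 7/245 = 2.86% (1.16–5.80) | 7/250 = 2.80% (1.13–5.68) | 12/250 = 4.80% (2.50–8.23) |
| 7 | 25 | 7/225 = 3.11% (1.26–6.30) | 7/250 = 2.80% (1.13–5.68) | 32/250 = 12.8% (8.92–17.59) |

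The last column is an arithmetic limit, not a forecast. With x = 2, c = 5 and a single missed event, the all-enrolled figure is 3/250 = 1.20% (0.25–3.47).

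**Step 4. Expected bias.** Let r = x/(250 − c) be the reported rate.

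- c = 5, x = 2: r = 0.816%. If exited subjects share this rate, 5 × 0.00816 = 0.041 missed events are expected and the bias is zero. At ten times the rate, 0.408 are expected, and the all-enrolled rate is (2 + 0.408)/250 = 0.963%, a gap of 0.15 percentage points.
- c = 13 (about 5%), x = 2: r = 2/237 = 0.844%. Expected missed events are 13 × 0.00844 = 0.110, with no bias. At ten times the rate, 1.097 are expected, and the all-enrolled rate is (2 + 1.097)/250 = 1.239%, a gap of 0.39 points.

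**Step 5. The other direction.** Suppose one of five crossing failures has an in-hospital event, the other four have none by day 30, and there are two events elsewhere. The report is 3/246 = 1.22% (0.25–3.52), against 3/250 = 1.20% over all enrolled. Here the reported rate is slightly too high.

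**The case against.** The strongest reply is that nothing here is contradictory. Section 9.4 says who belongs to the cohort, and Sections 9.1 and 9.5 say what is done when an outcome is missing. The exit is deliberate and its reason is given: no IVL was delivered. Sections 10.4.1 and 10.4.2 collect adverse events, including serious ones, from enrollment through 24 months without excepting crossing failures, and most MALE/POD components would be serious adverse events. Section 9.1 sends clarifications to the SAP, which may set a denominator rule. The exits are recorded as device deficiencies, and reporting the number of observations would show the smaller denominator. The effect is tiny on plausible figures, and there is no hypothesis test.

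Some of this stands. The numerical effect is likely small. The denominator rule is the natural reading of Section 9.1, not an explicit statement about these subjects. The scope is narrow: pre-dilatation must first be exhausted, and the reason given for exit suggests that a subject with two target lesions, one of them treated with IVL, would stay in follow-up, although the text does not settle this.

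The core is untouched. The reason for exit may justify dropping 24-month follow-up, but it does not reconcile Section 7.7.7 with an all-enrolled 30-day endpoint. Sections 10.4.1 and 10.4.2 set a collection period but no means of reaching a subject who has left, so they add a second inconsistency rather than supplying the data. A SAP can define a population or a denominator, but it cannot recover status that nobody obtained.

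**Conclusion.** The concern holds. Followed as written, the protocol places device crossing failures in the primary ITT cohort and then ends their observation before the primary safety endpoint is reached. The 30-day MALE/POD proportion would not be the ITT result that Section 9.4 describes, and the subjects lost are selected by device performance.

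The size rests entirely on assumed rates. With 5 exits and 2 observed events, the bias is zero if exited subjects have the same risk as the rest and about 0.15 points at ten times that risk. With 13 exits the latter figure is about 0.39 points. The direction is not fixed. The effectiveness endpoint is assessed at the end of the procedure and is unaffected, and no pass/fail decision depends on the safety figure. It should be fixed because it concerns a primary endpoint, the remedy is cheap, and the missing data cannot be recovered later.

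**What to change.** 1. Amend Section 7.7.7 and Table 1 so that day-30 MALE/POD status (vital status, above-ankle amputation, major reintervention) is obtained by one contact before a crossing-failure subject is exited.
2. Align Section 7.7.7 with Sections 9.4 and 10.4.1, so that population, follow-up and adverse-event collection agree. State whether the exit applies only to subjects who received no IVL in any target lesion.
3. For subjects already exited, report their number and give best-case and worst-case bounds over all enrolled subjects beside the observed-case result. Do not describe the observed-case denominator as all enrolled subjects.

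The cost is a protocol amendment, with IRB/EC approval where Section 11.6 requires it, and one contact each for a few subjects, provided their consent covers it. The consent template is a separate attachment (Section 17.0) and could not be checked. The bounds need no extra data. The change concerns data collection and reporting only and does not affect treatment.

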### 7.7.8 IVL Treatment

A full description of the IVL procedure is detailed in the Instructions for Use (IFU) including appropriate balloon sizing. Note that there are specific IFUs and labelling provided for the United States (US) and for Outside of the US (OUS).

Select an IVL balloon catheter size that is 1.1:1 based on balloon compliance chart and reference vessel diameter; the largest diameter balloon should be used if 1.1:1 sizing is not available.

Once the IVL balloon is placed in the target lesion area, the balloon must be inflated to 4 atm to deliver one cycle of IVL pulses. Table 2 lists the pulsing sequence for each IVL catheter. For the M and M5+ catheters, one cycle = 30 pulses; for the S4 catheter, one cycle = 20 pulses. Insertion of any size IVL Catheter into the IVL Generator will automatically program the IVL Generator with the appropriate treatment sequence. Note that the generator is programmed to force a minimum pause time of 10 seconds following every cycle.

Following delivery of the first IVL cycle, the balloon must be inflated to 6 atm (nominal pressure; refer to IFU) and record lesion response on fluoroscopy. Deflate the balloon and wait 10 seconds to re-establish blood flow. Repeat the steps above to complete a second cycle of pulses to complete a single treatment. Additional treatment cycles can be performed if deemed necessary.

	No.: CP 65007	REV. C
	TITLE: Disrupt PAD BTK II Study	
	CLASS: CLINICAL PROTOCOL	PAGE 33 OF 71

Additional pulses can be performed in a single location to obtain residual stenosis <50%. Multiple treatment locations should be done for long lesions with IVL balloon overlap of 1 cm. For optimal results, treat the entire lesion length with IVL; do not use “spot” IVL.

Caution: Care must be taken not to exceed 160 pulses in the same segment.

**Table 2. IVL System Sequence Chart**

	M 	M 5+	S 
Treatment Frequency	1 Pulse per Second	2 Pulses per Second	1 Pulse per Second
Maximum Number of Continuous Pulses (1 cycle)	30 Pulses	30 Pulses	20 Pulses
Minimum Pause Time (between cycles)	10 Seconds	10 Seconds	10 Seconds
Maximum Total Pulses Per Catheter	300 (10 Cycles)	300 (10 Cycles)	160 (8 Cycles)

### 7.7.9 Post-Dilatation

Post-dilatation with a semi or non-compliant PTA balloon catheter must be completed when post-IVL results in one of the following:

- Residual stenosis  $\geq 50\%$  by visual estimate, or
- Presence of a flow-limiting ( $\geq$ Grade D) dissection, or if
- Trans-lesional gradient  $>10\text{mm Hg}$  is observed.

Post-dilatation may also be performed per physician discretion. The physician should use a 1:1 balloon catheter to artery ratio and may post-dilate for several minutes. Follow the angiographic core lab guidelines to complete angiography showing all target lesions with reproducible landmarks for follow-up evaluation and assessment.

### 7.7.10 Assessment for Acute PTA Failure

Treatment with a stent or Tack implant is allowed for the following:

[figure not shown]
- Residual stenosis  $\geq 50\%$  by visual estimate, or
- Un-resolved flow-limiting ( $\geq$  Grade D) dissection, or if
- Trans-lesional gradient  $>10\text{mm Hg}$  is observed.

### 7.7.11 IVUS Assessment (optional Sub-study)

For subjects enrolled in the IVUS Sub-study, angiographic and IVUS images must be assessed at baseline, immediately post-IVL, and end of procedure. The core lab will provide a separate IVUS protocol to participating study centers.

	No.: CP 65007	REV. C
	TITLE: Disrupt PAD BTK II Study	
	CLASS: CLINICAL PROTOCOL	

**Figure 2. BTK IVL Treatment Algorithm**

## 7.8 Follow-Up

### 7.8.1 Discharge or Within 12-24 Hours Post-Procedure

The following assessments and procedures will be performed within **12-24 hours** post procedure or prior to hospital discharge, whichever occurs first:

- Adverse event assessment
- Review of medications (anticoagulants and antiplatelets)

### 7.8.2 30-Day Follow-Up

The following evaluations will be performed at **30 days** (+/-7 days) post procedure:

- Physical examination
  - Vital signs
  - Target review of symptoms
- ABI or TBI (at rest; keep consistent with screening)
- Rutherford Category
- VascuQoL-6 Questionnaire
- Wound Healing Assessment (including photographs)
- Review of medications (anticoagulants and antiplatelets)
- Adverse event assessment

	No.: CP 65007	REV. C
	TITLE: Disrupt PAD BTK II Study	
	CLASS: CLINICAL PROTOCOL	PAGE 35 OF 71

*Note: If treatment of two target lesions is planned across both limbs, the Rutherford Category and ABI/TBI for each limb must be assessed. If ABI/TBI cannot be assessed due to non-compressible vessels, this should be documented.*

### 7.8.3 6-Month Follow-Up

The following evaluations will be performed at **6 months** (180 +/-30 days) post procedure:

- Physical examination
  - Vital signs
  - Target review of symptoms
- ABI or TBI (at rest; keep consistent with screening)
- Rutherford Category
- VascuQoL-6 Questionnaire
- Wound Healing Assessment (including photographs)
- Review of medications (anticoagulants and antiplatelets)
- Adverse event assessment
- Duplex ultrasound (DUS)

*Note:*

- *If treatment of two target lesions is planned across both limbs, the Rutherford Category and ABI/TBI for each limb must be assessed. If ABI/TBI cannot be assessed due to non-compressible vessels, this should be documented.*
- *In the event of a non-diagnostic DUS, a 90-day extension is allowed on the upper limit of the window for the 6- and 12-month visits*

### 7.8.4 12-Month Follow-Up

The following evaluations will be performed at **12 months** (365 +/-30 days) post procedure:

- Physical examination
  - Vital signs
  - Target review of symptoms
- ABI or TBI (at rest; keep consistent with screening)
- Rutherford Category
- VascuQoL-6 Questionnaire
- Wound Healing Assessment (including photographs)
- Review of medications (anticoagulants and antiplatelets)
- Adverse event assessment
- Duplex ultrasound (DUS)

*Note:*

	No.: CP 65007	REV. C
	TITLE: Disrupt PAD BTK II Study	
	CLASS: CLINICAL PROTOCOL	PAGE 36 OF 71

- *If treatment of two target lesions is planned across both limbs, the Rutherford Category and ABI/TBI for each limb must be assessed. If ABI/TBI cannot be assessed due to non-compressible vessels, this should be documented.*
- *In the event of a non-diagnostic DUS, a 90-day extension is allowed on the upper limit of the window for the 6- and 12-month visits*

### 7.8.5 24-Month Follow-Up

The following evaluations will be performed at **24 months** (730 +/-30 days) post procedure:

- Physical examination
  - Vital signs
  - Target review of symptoms
- ABI or TBI (at rest; keep consistent with screening)
- Rutherford Category
- VascuQoL-6 Questionnaire
- Wound Healing Assessment (including photographs)
- Review of medications (anticoagulants and antiplatelets)
- Adverse event assessment

*Note: If treatment of two target lesions is planned across both limbs, the Rutherford Category and ABI/TBI for each limb must be assessed. If ABI/TBI cannot be assessed due to non-compressible vessels, this should be documented.*

### 7.8.6 Prior to Target Limb Revascularization

If a target limb procedure is performed during the follow-up period, angiographic images acquired as standard of care should be submitted to the core lab for purposes of adjudication.

## 7.9 Subject Withdrawal

A study subject has the right to discontinue participation at any time without penalty or loss of benefits to which the subject is otherwise entitled. A subject that has withdrawn from the study will be treated according to standard of medical care and will not be replaced.

Potential reasons for withdrawal from the study are, but not limited to:

- Subject lost to follow-up
  - Pregnancy
  - Subject meets exclusion criteria not previously recognized or newly developed
- Safety concerns regarding the device

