### 7.2.2 Exclusion Criteria

Subjects who meet any of the following exclusion criteria may not be enrolled in the study:

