#### General Exclusion Criteria

1. Rutherford Clinical Category 0, 1, 2, and 6 (target limb).
2. Subjects with osteomyelitis or deep soft tissue infection are excluded unless infection can be treated with an individual toe ray amputation or transmetatarsal amputation (TMA) in the target limb in the opinion of the investigator.
3. History of endovascular or surgical procedure on the target limb within the last 30 days, or planned within 30 days of the index procedure with the exception of toe amputation(s).
4. Subject in whom antiplatelet or anticoagulant therapy is contraindicated.
5. Subject has known allergy to contrast agents or medications used to perform endovascular intervention that cannot be adequately pre-treated.
6. Subject has known allergy to urethane, nylon, or silicone.
7. Myocardial infarction within 30 days prior to enrollment.
8. History of stroke within 60 days prior to enrollment.

	No.: CP 65007	REV. C
	TITLE: Disrupt PAD BTK II Study	
	CLASS: CLINICAL PROTOCOL	PAGE 25 OF 71

9. Subject has acute or chronic renal disease with eGFR <30 ml/min/1.73m^2 (using CKD-EPI formula), unless on renal replacement therapy.
10. Subject is pregnant or nursing.
11. Subject is participating in another research study involving an investigational agent (pharmaceutical, biologic, or medical device) that has not reached the primary endpoint.
12. Subject has other medical, social or psychological problems that, in the opinion of the investigator, preclude them from receiving this treatment, and the procedures and evaluations pre- and post-treatment.
13. Covid-19 diagnosis within 30 days.
14. The planned use of cutting/scoring balloons, re-entry or atherectomy devices in target lesions during the index procedure.
15. Planned major amputation (of either leg).
16. Acute limb ischemia (of either leg).
17. Occlusion of all the inframalleolar outflow arteries/vessels (i.e., desert foot) in the target limb.
18. Subject has an anticipated life span of less than one (1) year.
19. Subject already enrolled into this study.

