#### **Angiographic Exclusion Criteria**

20. Failure to treat clinically significant inflow lesions in the ipsilateral iliac, femoral, or popliteal arteries with ≤30% residual stenosis, and no serious angiographic complications (e.g., embolism).
21. Failure to successfully treat significant *non-target* infra-popliteal lesions prior to treatment of *target* lesion(s). Successful treatment is defined as obtaining ≤50% residual stenosis with no serious angiographic complications (e.g., embolism).
22. Treatment of vessels below the ankle joint.
23. Failed pre-dilatation in *target* lesion during index procedure with angiographic evidence of serious angiographic complications.
24. Target lesion includes in-stent restenosis.
25. Evidence of aneurysm or thrombus in target vessel.
26. No calcium or mild calcium in the target lesion.
27. Target lesion within native or synthetic vessel grafts.

	No.: CP 65007	REV. C
	TITLE: Disrupt PAD BTK II Study	
	CLASS: CLINICAL PROTOCOL	PAGE 26 OF 71

28. Failure to successfully cross the guidewire across the target lesion; successful crossing defined as tip of the guidewire distal to the target lesion in the absence of flow limiting dissections or perforations.

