### 7.9.1 When and How to Withdraw Subjects

Subjects may be withdrawn at the medical discretion of the physician, or they may voluntarily withdraw their consent at any time without impact to their medical treatment.

	No.: CP 65007	REV. C
	TITLE: Disrupt PAD BTK II Study	
	CLASS: CLINICAL PROTOCOL	PAGE 37 OF 71

Prior to enrollment, the investigative site should provide contact information and detailed instructions to subjects on how to withdraw from the study. When a subject is withdrawn, all data obtained prior to the time of withdrawal may be submitted to the Study Sponsor and be included in the study database, unless otherwise requested by the subject in writing.

In the event a subject is lost to follow-up or cannot be contacted for post-treatment assessments, at least three attempts (two phone calls and a certified letter) will be made to locate the study subject, and these efforts will be documented. If the subject cannot be located, the subject's lost to follow-up status will be documented in the EDC and they will be exited from the clinical study.

Should the subject expire, an adverse event form and a study exit/withdrawal form must be completed. Physician assessment is required to determine if the cause of death was possibly, probably, or definitely related to the IVL System. If available, copies of the death certificate and/or an autopsy report should be included in the research records. The Investigator may need to provide written notification to the IRB/EC upon the death of the study subject, dependent on the IRB/EC policies.

	No.: CP 65007	REV. C
	TITLE: Disrupt PAD BTK II Study	
	CLASS: CLINICAL PROTOCOL	PAGE 38 OF 71

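### Section 7.9 allows an enrolled subject to be withdrawn for newly meeting an exclusion criterion, and nothing requires that subject's day-30 MALE/POD status.

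*Combined protocol and SAP*

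**What the plan says.** Section 7.9 gives a non-exhaustive list of potential reasons for leaving the study. One is "Subject meets exclusion criteria not previously recognized or newly developed". Section 7.9.1 adds that a subject may be withdrawn at the physician's medical discretion. On data, it says that "all data obtained prior to the time of withdrawal may be submitted to the Study Sponsor" unless the subject objects in writing. The contact attempts it requires are for subjects who are lost or cannot be reached.

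Other sections bear on the same subjects:

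- Section 7.2.2 introduces the exclusion criteria with "Subjects who meet any of the following exclusion criteria may not be enrolled in the study".
- Sections 7.2 and 7.7.5 set enrollment at insertion of the IVL catheter over the guidewire.
- Section 9.4 makes the primary population ITT, meaning every enrolled subject.
- Section 9.2.1 defines the primary safety endpoint as death, above-ankle amputation or major reintervention at 30 days. Section 9.2 gives it an exact 95% interval.
- Section 9.1 takes missing data out of the denominator. Section 9.5 rules out imputation in the primary analyses.

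**The concern.** IVL is delivered in one index procedure. Taking a treated subject out of the study because an exclusion criterion appears afterwards spares that subject no device exposure. It only removes information.

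Some criteria describe deterioration of the limb. If a site uses the listed reason when a limb worsens, the subject may leave just before the amputation, reintervention or death that the primary safety endpoint counts. With status unknown, that subject drops out of both numerator and denominator, and the reported rate is too low. The reported number of observations would show that a subject is missing, but not what happened next. Later amputation and CD-TLR results could be affected in the same way, through missing data or censoring.

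The listed reason also sits badly with the rest of the protocol, which treats exclusions as conditions of entry and counts all enrolled subjects.

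**Working it through.** **Step 1. Which criteria can arise after enrollment and precede the composite?**

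| Exclusion (7.2.2) | Time anchor | Can it precede a 30-day event? |
|---|---|---|
| 16, acute limb ischemia | none | Yes: it can lead to thrombectomy/thrombolysis or amputation |
| 1, Rutherford 6 | none | Yes: it can lead to amputation |
| 15, planned major amputation | none | Possible reading, but section 15.1 treats an amputation decided on after the procedure as unplanned |
| 3, target-limb procedure planned within 30 days | tied to the index procedure | Weak |
| 25, thrombus in target vessel | an angiographic criterion checked at the index procedure | Weak |
| 7 and 8, myocardial infarction and stroke | before enrollment | No |

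The firm cases are 16 and 1.

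**Step 2. Does any section secure day-30 status after withdrawal?**

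- Sections 10.4.1 and 10.4.2 follow AEs and SAEs to resolution or stabilization. They do not say that this continues after withdrawal, and they do not ask for composite status at day 30.
- Section 7.9.1 requires an adverse event form and an exit form when a subject dies. It does not require vital status to be sought after withdrawal.
- Section 11.4 asks for the reason for withdrawal, not the outcome.

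None of these requires the composite status.

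**Step 3. Size.** The plan's enrollment figure reproduces: 225 / (1 − 0.10) = 250, which allows for 0.10 × 250 = 25 losses (section 9.3). A few exits of this kind would sit inside that allowance. The protocol gives no expected MALE/POD rate, so every event and exit count below is assumed.

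Let N = 250, let E be the true number of events, and let k be the would-be events withdrawn first with status unknown.

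- Rate with full ascertainment: E/N
- Rate as planned: (E − k)/(N − k)
- Shift per exit: [E/N − (E − k)/(N − k)]/k = (N − E)/[N(N − k)]

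| E | k = 1 | k = 2 |
|---|---|---|
| 2 | 248/(250 × 249) = 0.398 points | 248/(250 × 248) = 0.400 |
| 5 | 245/(250 × 249) = 0.394 | 245/(250 × 248) = 0.395 |
| 10 | 240/(250 × 249) = 0.386 | 240/(250 × 248) = 0.387 |

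Example with E = 5 and Clopper-Pearson 95% intervals:

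- Full ascertainment: 5/250 = 2.00% (0.65 to 4.61)
- One would-be event withdrawn first: 4/249 = 1.61% (0.44 to 4.06)
- Two withdrawn first: 3/248 = 1.21% (0.25 to 3.49)
- Four exits, none a would-be event: 5/246 = 2.03% (0.66 to 4.68)

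The last line shows that exits unrelated to outcome cause essentially no bias. All four intervals overlap.

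**Step 4. What could be said if status stayed unknown?** Take 3 observed events and count every unknown exit as an event:

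| Unknown exits | Dropped, as planned | All counted as events |
|---|---|---|
| 2 | 3/248 = 1.21% (0.25 to 3.49) | 5/250 = 2.00% (0.65 to 4.61) |
| 5 | 3/245 = 1.22% (0.25 to 3.54) | 8/250 = 3.20% (1.39 to 6.21) |
| 10 | 3/240 = 1.25% (0.26 to 3.61) | 13/250 = 5.20% (2.80 to 8.73) |

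The planned figure hardly moves as exits accumulate, so it gives no warning. The right-hand column is a worst-case bound, not an estimate.

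**The case against.** The best reply is that the protocol already treats these occurrences as outcomes. Acute limb ischemia or progression to Rutherford 6 would ordinarily be reported as an AE before any exit. If serious, it reaches the sponsor within 48 hours and is followed to resolution. Reasons for withdrawal must be sought (11.4), and inclusion/exclusion departures are major deviations (12.3). This stands as a narrowing of the gap. It does not close it, because nothing says that event follow-up survives withdrawal or yields day-30 composite status.

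A reader might infer that several more criteria feed the bias: a planned target-limb procedure, "Evidence of aneurysm or thrombus in target vessel", and planned major amputation. The text does not support that firmly. The first concerns procedures planned around the index procedure, the second is an index angiographic check, and section 15.1 works against the third. A reader might also infer that subjects who improve to Rutherford 0 to 2 would be withdrawn. That would defeat the Rutherford change endpoint scheduled to 24 months, so it counts against a literal reading of the listed reason and is not a likely practice.

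It is also fair to say that deleting the listed reason would close no exit by itself. The list is not exhaustive, and physician discretion remains. That stands, and it is why the remedy rests on data collection after withdrawal.

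Finally, sections 5.3 and 9.1 leave exploratory analyses and clarifications to an SAP. The text supplied contains only the section 9 plan, so a listing or sensitivity analysis specified elsewhere cannot be ruled out.

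**Conclusion.** The concern holds in a limited form. A stated rule permits, but does not require, exits that can be related to the primary safety outcome, and no section requires day-30 composite status afterwards. If such exits precede events, the 30-day MALE/POD rate is biased downward by 0.39 to 0.40 percentage points per would-be event at 250 enrolled, for 2 to 10 assumed true events.

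The frequency is not given and may be zero. A reader might infer that the safety result will be biased or a conclusion overturned. The documents support neither: withdrawal is optional, there is no safety hypothesis test, and the illustrative intervals overlap. The harm would be to the estimate. The primary effectiveness endpoint is read at the final procedural timepoint, so later exits do not affect it. The change is worth making because it is cheap and because the lost information could not be recovered by analysis.

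**What to change.** **Sections 7.9 and 7.9.1.** State that:

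- an eligibility finding after enrollment is handled under the deviation rules of 12.3 and does not end endpoint data collection;
- a subject withdrawn for any reason other than withdrawal of consent still has day-30 death, above-ankle amputation and major reintervention status collected, and stays in the ITT analysis.

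Reconcile two existing texts with this: the listed reason in 7.9, and the exit of device crossing failures after discharge in 7.7.7. The physician's discretion over clinical care is unchanged.

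**Section 9.5.** List every exit before day 30 by reason and known endpoint status. An analysis counting unknown exits as events is optional. If done, show crossing-failure exits separately and label the result a worst-case bound, since it can overshoot. With four exits, none a would-be event, and a true 5/250 = 2.00%, it gives 9/250 = 3.60% (1.66 to 6.72).

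**Cost.** A few lines of text, one table, and follow-up contact for a few subjects who would otherwise have left.
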